### 4.2. SECONDARY OUTCOMES

The secondary outcomes of the study will be:

- a. The number of days to physiologic maturity after randomization up to 48 wks PMA.  
Physiologic maturity will be defined as follows:
  - i. Temperature: out of the incubator for at least 48 hours with normal body temperature
  - ii. Feeding: oral feeding at a volume of at least 140 ml/kg for 48 hours or growing on less than 140 ml/kg/day for at least 48 hours
  - iii. Respiratory: apnea-free for at least 5 consecutive days
- b. Post-menstrual age (PMA) at discharge up to 48 wks PMA, censoring at time of transfer or death (status).
- c. The number of all-cause readmissions, including apneic events and apparent life-threatening events (ALTE), to the hospital within the first four weeks, second four weeks, and first eight weeks combined after discharge from the hospital by 48 wks PMA.  
An apparent life-threatening event is defined by the American Academy of Pediatrics as an event that is perceived by the observer as life-threatening. This event can include apnea, color change (cyanosis), profound change in muscle tone (hypotonia), gagging, and/or choking.
- d. The number of all-cause sick visits, urgent care, emergency rooms, or health care provider's office, within the first four weeks, second four weeks, and first eight weeks combined after discharge from the hospital by 48 wks PMA.
- e. Safety measures pre-hospital discharge
  - a. Weight gain from randomization until status (discharge up to 48 wks PMA, with censoring at time of transfer or death). The weight gain may also be assessed using percentiles including birthweight percentiles.
  - b. The number of days after randomization until status that infant had at least two consecutive heart rates >200 documented at least 3 hours apart (when infant not crying).
  - c. Treatment for high blood pressure initiated after randomization until status.
  - d. The number of episodes between randomization and status that infant was placed NPO for  $\geq 24$  hours.
  - e. The use of anti-reflux medications started between randomization and status
  - f. The number of days that significant apnea/bradycardia, as defined by documentation of infant receiving any of the following between randomization and status: open label caffeine, other methylxanthines, doxapram, CPAP or ventilatory support for apnea/bradycardia.

- g. The presence of documented and treated arrhythmias between randomization and status, not due to tachycardia or bradycardia.
- h. The onset of documented seizures, as defined by treating with anti-convulsants, between randomization and status
- f. Death

Apnea of prematurity (AoP) is defined by the AAP as cessation of breathing for  $\geq 20$  seconds or  $< 20$  seconds if accompanied by bradycardia and/or cyanosis in infants  $<37$  weeks GA.

However, individual study sites may vary in its definition, and for purposes of the study the diagnosis of AoP will be determined by the attending neonatologists in each hospital (apnea countdown as per local practice pre-specified for each hospital) and by the attending neonatologist on each specific infant. For the purposes of this study, significant apnea episodes are defined as apnea events receiving treatment ordered by the attending physician (e.g. re-starting caffeine, not just stimulation for example).

Evaluation of infants during the first four weeks, second four weeks, and first eight weeks combined after discharge from the hospital is done to determine whether there is a difference in secondary outcomes on caffeine (first four weeks after discharge), off caffeine (second four weeks after discharge), and in overall outcomes after discharge home (first eight weeks after discharge).

A short discussion on the hypothetical cost-savings by the reduction in number of days of hospitalization as a financial benefit of the trial's intervention (caffeine versus placebo) will be done at the conclusion of the trial.

#### **4.3. STUDY INTERVENTION**

We propose enrolling moderately preterm infants who are between  $33^{0/7}$  and  $35^{6/7}$  weeks GA (inclusive) who are being treated with caffeine for AoP and for whom plans are to discontinue caffeine. Once the infant has been screened for eligibility, consented, and the neonatologist has determined that caffeine will be stopped, infants will be eligible to be randomized if they can be started on the study medication within 72 hours after stopping caffeine. They will be randomized either to continuing caffeine citrate at a dose of 10 mg/kg/dose (5 mg/kg caffeine base) given daily (treatment group) or an equal volume of placebo given daily (placebo group), not less than 12 hours between doses, to continue during the hospital stay and for 28 days after hospital discharge. In-hospital dosages will be adjusted weekly based on weight. Post-discharge dosage will be based on weight obtained within 48 hours of discharge.

Trial Arms		Trial Intervention
Intervention Group	Caffeine	Caffeine citrate 10 mg/kg/day given once daily until 28 days after discharge
Control Group	Placebo	Placebo contains all of the excipients except for the active ingredient, caffeine citrate (a volume equivalent to 10 mg/kg of caffeine citrate) given once daily for 28 days after discharge.

The trial medication (caffeine citrate or placebo) will be weight-adjusted on a weekly basis until discharge. An apnea countdown will be done as per local practice before discharge. The duration of this countdown will be site dependent but pre-specified. Many infants may require hospitalization for observation after resolution of the apneas because of other discharge issues such as temperature control or feeding tolerance. If the attending neonatologist decides that re-initiation of open-label caffeine is clinically indicated, caffeine/placebo treatment per randomization will be put on hold until the physician decides to discontinue open label caffeine at which time, the infant will be treated as per randomization within 24-72 hours after open label caffeine is stopped. Infants on study medication who are still in the hospital at 44 weeks PMA will have the caffeine/placebo discontinued.

Prior to discharge, a weight obtained within the last 48 hours will be used to determine the post-discharge dosage for those infants continuing with caffeine citrate or placebo at home. Once deemed ready for discharge, the parent will be supplied with 28 numbered vials with oral caffeine citrate (intervention group) or placebo at an equivalent volume (placebo group). The parents will be educated by the research nurse, discharge nurse, physician, or pharmacist on storage and administration of study medication. Infants will be continued at home on the same dose of caffeine citrate or placebo for the first 28 days after hospital discharge. A member of the research team will contact the parents to obtain post-discharge information within 72 hours after discharge, once a week for the first 4 weeks, and biweekly during the weeks 5 to 8 after discharge.

#### **4.4. BLINDING/MASKING**

Caffeine citrate therapy or placebo, depending on the randomized treatment allocation, will be prepared by the study pharmacist for administration in the NICU. Study pharmacist will prepare daily doses of study drug (caffeine or placebo) for administration while in the hospital. At discharge, study pharmacist will dispense a 28-day supply of either caffeine or placebo vials for home administration. All other research staff and all health care staff and family members will be blinded to the treatment allocation. The study medication can be prepared by the research pharmacist within 48 hours of anticipated discharge date.

#### **4.5. POTENTIAL RISKS AND BENEFITS TO SUBJECTS**

##### **4.5.1. Current Standard of Care**

AoP is quite common in premature infants; 50% to 90% of infants with GA in the range of the proposed trial have AoP. A review of 100 infants in the NICU at University of Alabama at Birmingham showed that 37% of infants within this cohort were treated with a methylxanthine. This is similar to Neonatal Research Network data from the Moderately Preterm Cohort Study, which showed that approximately one-third of infants received caffeine therapy. AoP can lead to intermittent hypoxemia, and if prolonged, can precipitate bradycardia and hypotension, which may lead to hypoxic-ischemic neurological injury.

## Initiating Caffeine Therapy

Currently, infants of  $29\frac{0}{7}$  to  $33\frac{6}{7}$  weeks GA at birth are admitted to the NICU. There is some variation in the practice of treatment with caffeine for preterm infants. Caffeine treatment may be started prophylactically upon admission for some preterm infants. Data from the Cochrane meta-analysis showed no differences in outcomes between prophylactic caffeine and placebo. Another practice is to administer caffeine in preparation for extubation. This method was shown to reduce extubation failure (RR 0.48, 95% CI 0.32 to 0.71) within a week. In general, multiple studies have shown the benefit of caffeine therapy in decreasing apneic episodes. Therefore, the common practice is to give caffeine treatment to preterm infants who have apnea thought to be due to prematurity.

## Discontinuing Caffeine Therapy

There is a wide variation in practices for discontinuing caffeine therapy. Caffeine has a half-life of approximately 4 days (~100 hours) in preterm infants. After an infant no longer has apneic episodes for a variable amount of time, neonatologists opt to discontinue caffeine. Most neonatologists will observe infants in the hospital for at least five days following discontinuation of caffeine treatment, and this has been incorporated into this trial protocol.

## Discharge Home

The American Academy of Pediatrics guidelines deem preterm infants ready to be discharged once they have achieved three main competencies: the ability to grow on full oral feeds, the ability to maintain body temperature in a simulated home environment, and sufficient maturity of respiratory control to allow for safe discharge. However, even with these guidelines, there is still a wide variety of practice regarding discharge. In addition, although most infants have caffeine discontinued, there is still a subset of infants that are discharged home on caffeine. In a multicenter study by Eichenwald et al, 6% of infants aged 30-33 weeks PMA were discharged on methylxanthine treatment. This trial will help answer whether the practice of discharging moderately preterm infants on caffeine shortens hospitalization and reduces readmissions and sick visits and whether other aspects of physiologic maturity are responsible for delays in discharge.

### 4.5.2. Risks

Neofax, a pharmaceutical reference source, includes side effects of caffeine citrate such as vomiting and restlessness, as well as functional cardiac symptoms, all based on low level of evidence studies. In two randomized-controlled trials, the frequency of side effects between infants receiving caffeine and those in the placebo group did not differ. Data on these measures are not collected usually in clinical care or trials so we will not collect them.

In the largest caffeine trial to date, the Caffeine for Apnea (CAP) trial, decreased weight gain was reported in the caffeine group as compared to the placebo group in the first days of treatment. However, weight gain during the hospitalization did not differ between caffeine and placebo group infants. In a recent large, randomized controlled trial of high-dose (caffeine

citrate 20 mg/kg, twice the dose planned for this trial) versus normal-dose caffeine (caffeine citrate 5 mg/kg), tachycardia was more frequent but still relatively uncommon occurring in 4% in the high-dose group. There was no difference in any other adverse effects between groups including feeding intolerance despite the use of doses much higher than those that will be used in the current trial. Serious toxicity has been noted in patients who have inappropriately received overdoses of caffeine with blood levels exceeding 50 mg/L but are rare with correct dosing. The most recent Cochrane meta-analysis did not include an analysis of side effects related to the use of methylxanthines.

A small study of 16 premature infants evaluating the effects of caffeine citrate on cerebral blood flow showed that giving high doses (25 mg/kg/day; base 12.5 mg/kg caffeine) decreased cerebral blood flow as measured from the internal carotid artery, with a reduction of 17 % and 22% at 1 hour and 2 hours post administration of caffeine, respectively. Another study corroborated the findings of decreased cerebral blood flow with high doses but showed that at a dose of 10 mg/kg/day or less of caffeine citrate there was no effect on cerebral blood flow. The large Caffeine for Apnea trial which used doses up to 10 mg/kg/day showed that neurodevelopmental impairment was reduced with caffeine treatment. The proposed trial will be using caffeine citrate doses of 10 mg/kg/day so there is no concern regarding alteration of cerebral blood flow.

Premature infants are being discharged at an average PMA of approximately 36 weeks, according to a large multicenter study. Although the majority of infants have resolution of apnea by 40 weeks PMA, some studies suggest late resolution of apneas, up to approximately 44 weeks PMA (accounting for maturation of the respiratory center). There is a possibility that sub-clinical apneic episodes may occur at home and could potentially lead to re-admissions to the hospital or sick visits. This risk will be evaluated as a secondary outcome in the proposed trial.

The review of the literature did not show increased risk of death from administration of caffeine citrate. Infants enrolled in this trial will have the timing of discharge determined by the attending neonatologist. The trial will not deviate from the local practices in determining discharge criteria or discharge timing.

Infants that qualify for this study are at increased risk for death, disability, and/or poor neurodevelopment given their underlying prematurity. They are also at risk for developing other conditions related to prematurity including but not limited to apnea, bradycardia, respiratory distress syndrome, intracranial hemorrhage, retinopathy of prematurity, feeding intolerance, infection, and bronchopulmonary dysplasia. These are existing risks of prematurity regardless of whether they participate in this study or not.

We do not anticipate an increase in the risk of death or adverse outcomes for infants receiving either of the treatments provided in this study over and above those risks seen historically in similar infants. There may, however, be other unknown serious risks or risks associated with being in this study that we do not anticipate at this time.

Infants and their families may experience stress and emotional distress from their time in the NICU and participation in the trial. There is a potential loss of confidentiality should the patient information be lost, stolen, or inadvertently distributed.

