#### **3.1.2. Secondary Hypotheses**

In moderately preterm infants with resolved AoP, continuing caffeine therapy for 28 days after hospital discharge compared to placebo will:

- a. decrease the number of days to reach physiologic maturity from randomization to discharge up to 48 wks PMA.
- b. decrease the number of readmissions to the hospital related to apneic or apparent life-threatening events as well as all-cause readmissions within the first four weeks, second four weeks, and first eight weeks combined after discharge from the hospital by 48 wks PMA.
- c. decrease the number of sick visits related to apneic or apparent life-threatening events as well as all-cause sick visits to urgent care, emergency rooms, or health care providers within the first four weeks, second four weeks, and first eight weeks combined after discharge from the hospital by 48 wks PMA.
- d. be safe for continuing caffeine during the hospitalization and after discharge home without an increase in side effects or adverse events
- e. decrease the number of days of hospitalization from randomization to discharge, leading to a hypothetical cost-savings as a financial benefit of the trial's intervention

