#### **3.1.4. Secondary Specific Aims**

- a. To evaluate the effect of continuing treatment with caffeine citrate in the hospital on number of days to reach physiologic maturity from randomization to discharge up to 48 wks PMA.

- b. To evaluate the effect of treatment with caffeine until 28 days after hospital discharge on all-cause readmissions to a hospital (including apneic and/or apparent life-threatening events) within the first 8 weeks after discharge by 48 wks PMA.
- c. To evaluate the effect of treatment with caffeine until 28 days after hospital discharge on the number of all-cause sick visits to urgent care, emergency rooms, or health care provider's office (including apneic and/or apparent life-threatening events) within the first 8 weeks after discharge by 48 weeks PMA.
- d. To evaluate the side effects and adverse events of caffeine continuation in the hospital and after discharge up to 4 weeks post study drug administration.
- e. To assess the hypothetical cost-savings by the reduction in number of days of hospitalization as a financial benefit of the trial's interventions.

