- a. The administration of study medication at home by the parents without frequent missed doses
- b. Loss to follow up
- c. Inaccurate or missing information regarding re-admission to the hospital or to sick visits
- d. Inaccurate data collection on follow-up forms provided by the parents
- e. Side effects from the study medication

The trial will be approved by each institutional review board (IRB). Parental consent will be obtained for each infant enrolled. Safety is of upmost importance and will be monitored by the Data Safety Monitoring Committee (DSMC) when 25%, 50%, and 75% of the subjects complete the eight-week follow up period (or are lost to follow up). The trial will record side effects and adverse events will be reported to the DSMC periodically. Expedited serious adverse events will be reported per local IRB guidelines and to the NICHD and NRN Data Coordinating Center at RTI.

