Prior to discharge, a research nurse, physician, or pharmacist will educate the parents on storage and administration of the medication to the infant. Other instructions to the parents include preparation of daily dose and if a dose is missed, it may be given at any time on that day if the dose can be given at least 12 hours before the next day's dose is due. If it was not given at all, the parents will be instructed to discard the entire vial that was missed and record it on the medication form. If an infant spits or vomits after a dose is given, another dose should not be given on the same day. Follow-up forms (Medication and Follow up Forms) will be supplied to allow the parents to keep track of daily medication administration and missed doses. The parent will be given a stamped envelope to return the forms to the NRN research coordinator at the end of the 8 weeks. If the study site allows for the use of a gift card, it will be mailed to the parent or guardian when the documents are returned to the research coordinator. The gift card will encourage the family member to return the follow up documents at the end of the 8-week follow up period. Because it will be supplied at the end of the study period, it will have no consequences to the enrollment or treatment of the infant. In addition, the gift card does not constitute payment to the family member for any service provided as part of the trial.

Of note, infants who are deemed to require apnea monitoring at home after enrollment will be allowed its use and this will be noted on a follow-up form. Data from the home monitor recordings will not be used in the trial.

The NRN research coordinator and staff will obtain maternal demographics data including age, race, education, marital status, and parity. In addition, infant data will also be recorded, including weight at birth, randomization, and status; length/head circumference at birth and status; date of status; date of last apnea episode recorded after randomization; use of CPAP or mechanical ventilation; date of last NPO episode lasting >24 hours as well as the number of episodes of NPO >24 hours following randomization; date of last orogastric or nasogastric feed; date of last day in incubator; dates of initiation and termination of open label caffeine therapy; and information related to side effects and adverse events.

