### **6.3. DATA MONITORING PLAN**

#### **6.3.1. Monitoring for Side Effects and Adverse Events**

Any infant that develops side effects or minor adverse effects related to the intervention can be continued on study medication at the discretion of the attending physician but the event will be recorded for the trial. If the infant demonstrates tachycardia of 220 beats per minute for greater than 60 minutes, the clinical team should hold the study drug for 24 hours. If tachycardia resolves, the study drug may restart.

Enrolled infants will have their inpatient record reviewed by research coordinators to obtain the following data:

- Infant weight: at birth, day of randomization, and status
- Heart rate: Number of days after randomization until status that there were at least two consecutive heart rates documented over 200 bpm (when infant was not crying) at least 3 hours apart
- Treatment for high blood pressure initiated after randomization until status
- Gastrointestinal issues (NPO for more than 24 hours)
- Use of reflux medications at status

In the largest caffeine trial, the Caffeine for Apnea trial, initial decreased weight gain was reported in the caffeine group as compared to the placebo group but with continued caffeine treatment, long-term weight gain did not differ between caffeine and placebo group infants. Differences in weight gain from the day of randomization, day of discharge (status), and at the infant's well child visits (e.g. one and/or four week periods discharge) will be monitored

Apnea/bradycardia:

The trial will allow for individual study sites to continue their standard practice, and the definition of AoP will be left at the discretion of the neonatology staff treating the infant. If an infant develops apnea, treatment will be left at the discretion of the attending neonatologist or institution. The etiology of the ensuing event and its management (e.g. CPAP, mechanical ventilation, sepsis) will be recorded. Apnea and bradycardia are common in eligible infants even with caffeine treatment and will not be considered serious adverse events.

Other complications of prematurity that are not likely to be related to the intervention will also be collected following randomization into this trial. These include development of necrotizing enterocolitis, intraventricular hemorrhage, periventricular leukomalacia, late onset sepsis, and severe retinopathy of prematurity.

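### The protocol declines to collect caffeine's listed side effects while hypothesising no increase in them; the gap is real for restlessness, vomiting and tolerability at home, but not for in-hospital cardiac effects

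*Protocol*

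**What the plan says.** Protocol 4.5.2 (Risks) reports that a pharmaceutical reference "includes side effects of caffeine citrate such as vomiting and restlessness, as well as functional cardiac symptoms". It adds that the evidence behind that list is weak and that two randomized trials found no difference from placebo in side-effect frequency, and concludes: "Data on these measures are not collected usually in clinical care or trials so we will not collect them".

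Other sections point the other way:

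- Protocol 3.1.2, hypothesis (d), expects treatment to "be safe for continuing caffeine during the hospitalization and after discharge home without an increase in side effects or adverse events".
- Protocol 3.1.4, aim (d), repeated as aim 4 in SAP 3.1.2, is: "To evaluate the side effects and adverse events of caffeine continuation in the hospital and after discharge up to 4 weeks post study drug administration".
- Protocol 3.4 states: "The trial will record side effects and adverse events will be reported to the DSMC periodically". Protocol 6.3.1 and SAP 7.4 make similar statements.
- Protocol 5.2.3 includes "information related to side effects and adverse events" among the infant data that staff record, and SAP 4.8 repeats this.
- Protocol 6.3.1 says that an infant with side effects or minor adverse effects related to the intervention may stay on study medication "at the discretion of the attending physician but the event will be recorded for the trial".

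The prespecified safety outcomes (Protocol 4.2, SAP 10.2) do include related items, for example: "The number of days after randomization until status that infant had at least two consecutive heart rates >200 documented".

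**The concern.** One section says that the drug's listed side effects will not be collected; the others say that side effects are evaluated, recorded and hypothesised not to increase. A coordinator who sees vomiting or restlessness thought to be related to study drug has an instruction to record it (6.3.1) and a statement that it is not collected (4.5.2). Sites may settle this differently.

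At stake is what the final report may say. If an effect is never asked about, finding no excess of it reflects non-collection rather than evidence. This matters most at home. Protocol 3.4 justifies the trial partly by the lack of safety data on late-hospital and home methylxanthine treatment, and the home period is the less observed part of the regimen.

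**Working it through.** The plan gives no figure on this point, so the check is an item-by-item comparison of each listed effect with the data the documents describe.

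| Listed effect | Described in hospital (Protocol 4.2 and 6.3.1; SAP 10.2) | Described at home (Protocol 6.3.1 and 6.3.2; SAP 8.3) |
|---|---|---|
| Functional cardiac symptoms | Days with repeated heart rates above 200; treated arrhythmias; treatment started for high blood pressure | No direct item; seen only through a recorded visit, admission or new medication |
| Vomiting | No direct item; proxies are NPO for at least 24 hours and anti-reflux drugs started | No direct item; seen only by the same routes |
| Restlessness | No measure or proxy | No direct item; at most a stated reason for a visit |

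**Time window.** Protocol 4.2 and SAP 3.2.2 label the safety measures as pre-discharge. Dosing continues for 28 days after discharge (Protocol 4.3), and aim (d) runs to 4 weeks after study drug. The aim therefore covers about 28 + 28 = 56 days at home, over which none of the listed safety measures applies.

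**Home data.** Families supply weights, reasons for visits and admissions, and final diagnoses (6.3.1), plus doses given or missed and new medications (6.3.2). No side-effect item is described. Yet Protocol 5.2.3 tells parents not to repeat a dose that day if the infant spits or vomits, so vomiting at home is foreseen.

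**Formal monitoring.** The interim safety endpoint (Protocol 6.3.3, SAP 7.4) counts events related to apnea of prematurity, not drug side effects.

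**SAP.** Section 10.1 promises the frequency of toxicities potentially attributable to treatment. Section 10.2 has no row for vomiting or restlessness. Section 10.3 limits the adverse event log to specific events but does not list them. Section 13 reports no changes from the protocol.

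**What solicited items would yield.** No document gives a rate, so the rate p is an assumption. With the plan's minimum of n = 439 per arm (Protocol 6.1), the 95% half-width for the difference between arms at a common rate is 1.96 × √(2p(1−p)/n):

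- p = 0.05: 1.96 × √(0.095/439) = 2.9 percentage points
- p = 0.10: 1.96 × √(0.18/439) = 4.0
- p = 0.30: 1.96 × √(0.42/439) = 6.1
- p = 0.50: 1.96 × √(0.50/439) = 6.6

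After the plan's 5% attrition (0.95 × 439 ≈ 417 per arm), the first two become 3.0 and 4.1.

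The schedule provides 1 + 4 + 2 = 7 post-discharge contacts if the 72-hour contact is counted separately. Five fall in the first four weeks, during dosing, and two in weeks 5 to 8, after it.

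**The case against.** The best defence is that 4.5.2 is a discussion of risk, not a procedure. It can be read as declining routine solicitation of non-specific infant symptoms, while 6.3.1 covers events judged related to the intervention. The protocol lists an Adverse Events Form (9.9), the SAP plans an adverse event log, and the forms appear only as titles, so their items cannot be checked. The sponsor also gives reasons: weak evidence for the listed effects, two randomized trials without a difference, and a dose-comparison trial without a difference in feeding intolerance. SAP 7.7 makes safety p-values descriptive, so no confirmatory test of no increase is planned.

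Much of this stands. Not soliciting common symptoms is partly a design judgement, and sites have usable instructions for related events. But the defence supplies a distinction between solicited and related events that the text never draws. Its own evidence also weakens the claim that such data are not usually collected in trials, since the section cites trials that compared them. A descriptive analysis still cannot describe an effect on which no data were sought.

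Two stronger readings are tempting. A reader might infer that nothing is collected on any of the three effects. The documents do not support this: tachycardia days, treated arrhythmias and blood-pressure treatment are prespecified in-hospital outcomes, and vomiting has two in-hospital proxies. A reader might also infer that no safety conclusion is possible. That does not follow either. Weight gain, the cardiac items, NPO episodes, anti-reflux drugs, significant apnea, seizures, serious adverse events, death, and post-discharge visits and readmissions are all collected and can be reported.

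**Conclusion.** The contradiction between Protocol 4.5.2 and Protocol 3.1.2(d), 3.1.4(d), 3.4, 5.2.3 and 6.3.1 is real, and the SAP leaves it open. Its consequence is limited to three areas: restlessness, which has no measure; vomiting, which has only in-hospital proxies; and tolerability at home, where effects surface only through a recorded visit, admission or new medication. For these, a general statement of no increase in side effects would be unsupported. A statement confined to the collected measures would be sound.

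This rests on the data items described in the text. If the unseen forms already carry vomiting or restlessness items, the data gap shrinks, but 4.5.2 and SAP 10.2 would then be wrong as written. The half-widths of 2.9 to 6.6 points depend on assumed rates of 5% to 50%. They show only that solicited items would be informative, not how often the symptoms occur.

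**What to change.** Reconcile Protocol 4.5.2 with 3.1.2(d), 3.1.4(d), 3.4, 5.2.3 and 6.3.1 by one of two routes.

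(a) **Narrow the claim.** Restrict hypothesis (d), aim (d) and SAP aim 4 to the safety measures actually collected, align the general statements that side effects are recorded, and list the specific adverse events in SAP 10.3. This costs only wording, and it is the route that remains if data collection has largely finished.

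(b) **Collect the items.** Delete the final clause of the 4.5.2 sentence. Add yes/no items for vomiting and restlessness to the In-hospital Outcomes Form (9.8) and the Post-discharge Study Drug and Medical Visit Form (9.11), ask them at the scheduled contacts, add them to SAP 10.2 and tabulate them by arm. The cost is a few questions and one table. The drawback is that parent-reported symptoms are non-specific, although blinding protects the comparison between arms. Report the first four weeks (on study drug) separately from weeks 5 to 8 (off study drug).
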